Duration of an individual subject's active participation:

2 weeks

Duration anticipated to enroll all subjects:

1 year

Estimated date for the investigator to complete this study (complete primary analyses):

9/30/2019

5. List the inclusion criteria:

Patients of [name], the PI, with the following:

1. Thumb CMC arthritis
2. greater than or equal to age 18
3. Interested in non-operative treatment of thumb arthritis

6. List the exclusion criteria:

1. Recent corticosteroid injection into the thumb joint
2. Non-English speaking
3. skin lesions or rashes on the thumb
4. current use of topical anti-inflammatory medications
5. concomitant thumb/wrist diagnoses that would impact the results (as determined by the PI)
6. known allergy to magnesium

7. Will children or any gender, racial or ethnic subgroups be explicitly excluded from participation?

Yes No

* Identify the subgroups and provide a justification:

Children - arthritis of the thumb CMC joint does not typically exist in subjects less than the age of 18 and including a rare patient that might have CMC arthritis would bias our results.

8. Describe the power analysis used and cite your method of statistical analysis. If a power analysis is not possible, thoroughly justify the sample size required for the study, including appropriate literature citation (alternatively provide page reference in attached protocol):

The mean pain reported in subjects with CMC arthritis is 5 (out of 10) on the numeric pain rating scale. Assuming a clinical meaningful change in pain of 2 on this scale, an alpha of 0.05 and beta of 0.2, the power analysis demonstrates 16 subjects required per group. Assuming a drop out rate of 20%, we will enroll 20 subjects per group.

Research Activities

- 1. * Provide a detailed description of all research activities (including screening and follow-up procedures) that will be performed for the purpose of this research study. This description of activities should be complete and of sufficient detail to permit an assessment of associated risks.**

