Screening and Enrollment: Patients diagnosed with thumb CMC OA by the PI and recommended for participation in the study will be assessed for inclusion and exclusion criteria appropriateness by the study coordinator. If they are candidates, consent will be obtained by the PI in a private room and they will be randomized into treatment or control group by the coordinator. At this time, the x-ray taken during routine care by the PI for diagnosis will be obtained and graded for severity.

Demographic information including age and gender will also be collected.

Research Visits: Baseline, 1 week and 2 week visits

Study procedures will be performed by the study coordinator in a patient room equipped with a hand table, if necessary, patient will be moved to an procedure room similarly equipped. Numeric Pain Rating Scale (NPRS), and Disabilities of the Arm, Shoulder, and Hand (DASH) will be administered to the participant by the study coordinator. Static range of motion will be tested with a wrist goniometer measuring flexion, extension, ulnar deviation, and radial deviation with the participant's elbow supported on a hand table. Strength testing will be performed with a hand dynamometer and pinch meter. These questionnaires/tests will be performed at the baseline, 1 week and 2 week visits. They should take approximately 10 minutes to complete. Study coordinator will also provide the participant with the foam and compression wraps and provide instructions for its use. The compression wrap is a cloth wrap (similar to an elastic bandage wrap) that will be saturated/treated with the Theraworx foam. Participants will be asked to apply the foam treated wrap nightly for a minimum of 6 and maximum 10 of hours and avoid use of lotions, topical creams, or topical NSAIDs during the study period. A study data sheet will be given at this time for the participant to document nightly compliance hours, daily Tylenol use, and daily pain rating. This sheet will be collected at the 2 week visit. This portion of the research visit should take approximately 5 minutes but will allow for time for questions.

- 2. Upload a copy of all materials used to collect data about subjects: (Attach all surveys, interview/focus group scripts, and data collection forms except for case report forms, SCID or KSADS):**

Data

Collection

10/9/2018 History

Data

Collection

10/9/2018 History

Data

Collection

9/30/2018 History

3. * Will blood samples be obtained for research purposes? Yes No

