Infrequent Risks	Isometric strength testing may result in muscle cramping, discomfort, or fatigue, although occurrence is rare (occurs in less than 1% of people).
Other Risks	No Value Entered

Research Activity	Randomization
Common Risks	Those being randomized to the placebo may not receive direct benefit compared to those randomized to foam.
Infrequent Risks	No Value Entered
Other Risks	No Value Entered

Research Activity	Use of Foam
Common Risks	No Value Entered
Infrequent Risks	Skin irritation, allergic reaction
Other Risks	No Value Entered

Research Activity	Storage of Research Data
Common Risks	No Value Entered
Infrequent Risks	Breach of Confidentiality
Other Risks	No Value Entered

Research Activity	Range of Motion Testing
Common Risks	No Value Entered
Infrequent Risks	The range of motion procedures may result in soreness, however it is rare (occurs in less than 1% of people).

2. * Describe the steps that will be taken to prevent or to minimize risks:

Subject research records will be double-locked, with access only by research personnel listed. Electronic files will be stored in password protected systems. Subject research records and the data linking file will be destroyed after 7 years to decrease the risk of confidentiality being breached.

Subjects will be instructed to not exert themselves in a manner that will cause pain during the procedures. Those who experience any pain or discomfort during the testing procedures will be given the opportunity to rest or terminate the testing session.

Subjects with any prior adverse reactions to topical agents will be excluded. In the event of any adverse event or injury, the investigator will provide the subject for proper medical treatment.

3. Financial risks - will the subject or insurer be charged for any research required procedures?

Yes No

4. Describe the steps that will be taken to protect subjects' privacy:

Examination and testing will be completed in a private examination room

5. What steps will be taken in the event that a clinically significant, unexpected disease or condition is identified during the conduct of the study:

The PI will notify the patient and either treat the condition or provide an appropriate referral.

6. Describe the potential benefit that individual subjects may experience from taking part in the research or indicate if there is no direct benefit. Do not include benefits to society or others:

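### The risk section promises to exclude people with prior adverse reactions to topical agents, but the exclusion list has no such criterion, so they could be enrolled and given foam

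*Combined protocol and SAP*

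**What the plan says.** Four parts of the combined protocol and SAP bear on this point.

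- **Risk and Benefits, item 2** asks what will be done to prevent or minimize risks. Part of the answer is an unqualified eligibility rule: "Subjects with any prior adverse reactions to topical agents will be excluded".
- **Study Design, item 6** is the formal exclusion list. It has six entries, and the only one about allergy is "known allergy to magnesium".
- **Research Activities, item 1** describes screening. Patients whom the PI has diagnosed and recommended "will be assessed for inclusion and exclusion criteria appropriateness by the study coordinator"; the PI then obtains consent and the coordinator randomizes.
- **Study Design, item 2** defines three arms: active foam with wrap, placebo foam with wrap, and active foam alone. The risk table (Risk and Benefits, item 1) lists skin irritation and allergic reaction as infrequent risks of foam use.

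**The concern.** An exclusion protects participants only if the person doing the screening is told to apply it. Here the rule appears in the answer about risk and not in the list that defines eligibility. A coordinator working from that list has no prompt to ask about past reactions.

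Two things are at stake. First, the protocol tells the IRB that a group at possibly higher risk of a skin reaction is kept out, while the operative criteria would let that group in. Because every arm in Study Design, item 2 involves a foam, allocation to the comparator does not avoid exposure to a topical product. Second, the enrolled population may differ from the one described, and anyone reading the results would not know which eligibility rule had been applied.

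**Working it through.** No arithmetic applies, and the plan states no figure to reproduce. The check is whether any listed criterion, or any described screening step, covers a history of adverse reactions to topical agents.

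**The six exclusions (Study Design, item 6):**

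1. "Recent corticosteroid injection into the thumb joint": a recent procedure. Does not cover it.
2. "Non-English speaking": language. Does not cover it.
3. "skin lesions or rashes on the thumb": a skin condition at one site, not a history of reacting to a product. Does not cover it.
4. "current use of topical anti-inflammatory medications": present use, not a past reaction. Does not cover it.
5. Coexisting thumb or wrist diagnoses: this gives the PI discretion, but only over diagnoses at those sites that would affect the results. Does not cover it.
6. "known allergy to magnesium": allergy to one substance. Overlaps in part, but is far narrower than any reaction to any topical agent.

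None of the six states the risk-section rule, and one overlaps with it in part.

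**The three inclusions (Study Design, item 5):** thumb CMC arthritis, adult age, and interest in non-operative treatment. None covers it.

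**The screening step (Research Activities, item 1):** the coordinator checks the inclusion and exclusion criteria. No further question about topical reactions is described.

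**Other safeguards in Risk and Benefits, item 2:** these concern record security, discomfort during testing, and medical care after an event. The exclusion is the only step in that answer that acts before exposure and is aimed at foam reactions.

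**Putting these together:** take a candidate who once reacted to a topical product, has no known magnesium allergy and no thumb rash or lesion, and otherwise qualifies. The risk section says this person is kept out. The listed criteria admit the person, who can then be assigned to any of the three foam arms.

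**The case against.** The strongest reply is that the rule is written in the same application, without qualification, and may be applied in practice. The PI recommends patients and obtains consent, and could ask about past reactions. The data-collection attachments are listed under Research Activities, item 2, but their content is not available for review, so a form may already contain the question. This stands, and it limits the claim: such people *could* be enrolled. A reader might infer that they *would* be, or that the safeguard is not applied. The documents do not establish either. They do show that no described step carries the rule into screening, and a check that rests on informal practice is hard to verify afterwards.

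A second reply is that the hazard is small. Study Aims, item 2 reports no allergic reaction and no irritation in previous studies of the foam, and the risk table classes these events as infrequent. That lowers the likely harm but does not remove the contradiction, since the protocol still lists the risk and still promises the exclusion.

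A third reply is that an allergic reaction is already handled as a ground for withdrawal (Risk and Benefits, item 7). That acts only after exposure and does not replace screening. Nor should it be read the other way. A reader might infer that a reaction means a missing 2-week score, but the protocol describes withdrawal as something that might happen, and item 8 keeps data already collected.

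A reader might also infer that the magnesium criterion is misplaced because the background does not name magnesium. The background gives selected ingredients and does not claim to be a full list, so that does not follow.

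Finally, Basic Information, item 3 describes a control group using a wrap and mentions no foam. The statement that every arm receives foam rests on the three-arm design in Study Design, item 2.

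**Conclusion.** The inconsistency is real and can be shown from the documents alone. An exclusion claimed as a risk-minimization step is absent from the eligibility list and from the described screening procedure, so people it is meant to keep out could be enrolled and given a foam in any arm.

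Its size cannot be stated. The documents give no frequency of prior topical reactions, and any count out of the 60 participants would rest on an unsupported rate. The conclusion assumes that screening follows the list in Study Design, item 6, and that the arms are those in Study Design, item 2.

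The point concerns participant safety and the description of the population. It has no bearing on the sample size or the ANOVA, and the documents give no ground for expecting bias between arms from it. It should be corrected, but it does not threaten the validity of the comparison.

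**What to change.** Before enrolment, reconcile Study Design, item 6, Research Activities, item 1 and Risk and Benefits, item 2 so that all three state the same eligibility rule. There are two routes, and the investigator decides between them:

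- carry the risk-section exclusion into the formal list and into the screening step, after checking whether the existing forms already ask the question; or
- remove the statement from the risk section if it is not intended as a criterion.

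This review does not say which rule is right. The cost is about one line of text. If the first route is taken, a few candidates may also be screened out.

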*** Describe the circumstances and any procedures for orderly termination:**
unforeseen illness or allergic reaction to foam or non-compliance

8. Describe procedures that will be followed when subjects withdraw from the research, including partial withdrawal from procedures with continued data collection and data already collected:

The data already collected will continue to be used in the study.

Placebo Arm

1. * Is there a commonly used diagnostic/treatment approach that is currently recognized as being effective for the proposed subjects' disease or condition, and that will be withheld from subjects assigned to the placebo arm of this research study:

Yes

2. Describe the commonly used diagnostic/treatment approaches that will be withheld from subjects assigned to the placebo arm of this research study:

A commonly used treatment approach is corticosteroid injection, over the counter pain medications, and/or surgical treatment.

3. Is enrollment into this study limited to individuals in whom the commonly used diagnostic/treatment approaches are known to be ineffective or intolerable?

no

4. Provide a scientific justification for the placebo-control arm of this research study:

The study purpose is to compare the use of TheraWorx foam and compression wrap, with the placebo foam with wrap and Theraworx foam alone on subjects with thumb carpometacarpal osteoarthritis having thumb or wrist pain.

5. How long will subjects participate in the placebo arm? Justify why this duration is necessary:

2 weeks. This is a short period of time. If no benefit in the placebo arm, can efficiently undergo other treatment options such as steroid injection.

6. How frequently will the subject's condition or disease be monitored and compare that to the frequency of monitoring associated with standard care for this disease/condition?

weekly

7. What specific endpoints will result in discontinuing a subject's participation due to worsening of the subject's disease or condition?

It is such a short study and examining a chronic condition (arthritis) that the PI does

not expect an acute worsening of the disease or condition.

8. What is the risk to subjects who receive no active treatment for their disease or condition while in the placebo arm?

Delay in treatment by usual care conservative measures resulting in pain

9. Describe the planned involvement of a 'contact person' who interacts with the subject on a regular basis and who will notify the investigators immediately of any problems related to the subject's disease or condition:

There is no reason why the subject could not contact the investigators in this study on thumb arthritis. No plans to involve a contact person.

Note: The involvement of the contact person must also be addressed in the consent form

Statistical Analysis Plan

The Primary Outcome is VAS pain score at 2 weeks

This will be analyzed with ANOVA which is the appropriate test for continuous data and multiple groups.

Significance will be set at 0.05

Secondary Outcomes

Will also be analyzed using ANOVA.

Significance will be set at 0.05

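### Participants may be withdrawn for undefined non-compliance with no assessment planned afterwards, and the SAP names no analysis set, so the primary ANOVA may exclude non-compliers

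*Combined protocol and SAP*

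**What the plan says.** Risk and Benefits, item 7, lists the circumstances for withdrawal without consent as "unforeseen illness or allergic reaction to foam or non-compliance". It gives no definition of non-compliance, no threshold and no timing.

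Item 8 asks what happens on withdrawal, including the case where procedures stop but data collection goes on. The whole answer is: "The data already collected will continue to be used in the study".

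The Statistical Analysis Plan states: "The Primary Outcome is VAS pain score at 2 weeks". The method follows: "This will be analyzed with ANOVA which is the appropriate test for continuous data and multiple groups". It names no analysis set, makes no intention-to-treat statement and gives no rule for missing scores.

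Other relevant places:
- Study Design, item 2: three arms, of which two use foam with a compression wrap and one uses foam alone. Assessments are at baseline, week 1 and week 2.
- Study Design, item 2, and Research Activities, item 1: participants record nightly hours on a sheet that is handed in at the 2-week visit.
- Data Safety and Monitoring, item 1: the investigator and coordinator meet monthly to check compliance. The same item later calls these meetings weekly.

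**The concern.** Compliance is behaviour that follows randomisation. A rule that lets non-compliers be taken out of data collection allows that behaviour to decide who has a primary outcome. Keeping earlier data does not replace a 2-week score that was never taken, and neither baseline adjustment nor a longitudinal model recovers a measurement that the protocol stopped collecting.

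The loss matters most if it is uneven. Wearing a wrap for 6 to 10 hours a night is a burden that the foam-alone arm does not carry, so non-compliance may be more frequent in the two wrap arms. If those removed also have more pain than those who stay, the wrap arms look better than they should against foam alone. Foam with wrap against foam alone is one of the comparisons named in every hypothesis under Study Aims.

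**Working it through.** **1. The plan's own figure.** Study Design, item 8, gives a difference of 2 points, alpha 0.05 and beta 0.2, and states that "the power analysis demonstrates 16 subjects required per group". No SD is given. Assuming SD 2 and a two-sided test, n = 2 × (1.960 + 0.842)² × SD² / difference² = 2 × 7.85 × 4 / 4 = 15.7, so 16. With 20% dropout, 16 / 0.80 = 20 per arm. Both figures reproduce under that assumption; 80% power with exactly 16 corresponds to an SD of about 2.02.

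**2. Following a non-complier through the documents.**
- *Noticed before week 2, for example at the week-1 visit, and withdrawn:* item 8 keeps baseline and week-1 data. No 2-week assessment is planned, so the participant is absent from the primary ANOVA.
- *Noticed from the sheet at the 2-week visit:* the score can be taken at that visit, and once taken, item 8 keeps it. The SAP does not say whether the participant is analysed, so that choice could be made after the outcome is known.

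**3. Size of the shift.** Let q be the share removed in an arm and g the amount by which removed participants would have scored worse than those retained. With no true effect, each arm's completers have mean (overall mean − q × g), so the spurious difference between two arms is g × (difference in q). Assume 30% removed in each wrap arm and 10% with foam alone:

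| g (points) | shift = g × (0.30 − 0.10) | share of the 2-point target |
|---|---|---|
| 1 | 0.2 | 10% |
| 2 | 0.4 | 20% |
| 3 | 0.6 | 30% |

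**4. Effect on the three-arm F test.** From 20 per arm, 14, 14 and 18 remain (46 in total, 2 and 43 degrees of freedom, 5% critical value 3.21). The noncentrality is (28 × 18 / 46) × shift² / SD² = 10.96 × shift² / SD².

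| shift | noncentrality, SD 2 | type I error, SD 2 | type I error, SD 1.8 | type I error, SD 2.5 |
|---|---|---|---|---|
| 0.2 | 0.11 | 5.8% | 6.0% | 5.5% |
| 0.4 | 0.44 | 8.2% | 9.0% | 7.0% |
| 0.6 | 0.99 | 12.6% | 14.5% | 9.7% |

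A simulation (20 per arm, SD 2, 5,000 runs) agrees: 30/30/10% removed with g = 2 gave 8.5%. Keeping everyone in the analysis gave 4.5% to 5.5% across all scenarios tried.

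**5. Equal removal.** With 20% removed in every arm and g = 2, the shift is 0 and the simulated type I error was 4.8%. The cost is then power. By the formula of step 1 (difference 2, SD 2), pairwise power is 0.885 with 20 per arm, 0.807 with 16, 0.754 with 14 and 0.688 with 12. The 20% allowance leaves exactly 16, so removals for non-compliance would have to fit inside it together with ordinary dropout.

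**The case against.** The best case for the plan is timing. Participation lasts two weeks, the compliance sheet comes in at the visit where the primary score is taken, and compliance meetings are described as monthly. Much non-compliance would therefore surface when the score is already available, and item 8 would then retain it. This stands and narrows the problem. It does not remove it, because participants are also seen at week 1, the monitoring section is inconsistent about the interval between meetings, and the SAP does not say how late-detected non-compliers are handled.

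Three stronger readings are tempting and are not supported:
- *That the primary ANOVA is a compliers-only analysis by rule.* Item 7 asks when participants might be withdrawn. Nothing says that every non-complier is removed or that an existing score is discarded.
- *That wrap burden biases the placebo comparison.* Both wrap arms share the same described regimen, so the argument reaches only comparisons with foam alone and the overall F test. Removal could differ between the wrap arms for other reasons, but the documents give nothing from which to judge that.
- *That withdrawals are decided by staff who know the allocation.* The coordinator randomises and hands out the product, but no passage says who decides withdrawals or whether that person knows active from placebo foam.

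It is also fair to say that non-compliance might mean missed visits, where deleting the word recovers no data, and that withdrawals for illness or allergic reaction lose the same score. The remedy therefore has to cover stopping for any reason.

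**Conclusion.** The concern holds in a limited form. The protocol permits removal for undefined non-compliance and plans no assessment afterwards, and the SAP does not say who is analysed. The primary comparison may therefore exclude non-compliers, and could do so unequally between the wrap arms and foam alone.

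The existence of the gap is clear from the text; its size is not. The removal rates, the pain gap and the SD are all assumptions. The lowest scenario (5.8%) is close to nominal and the highest shown at SD 2 (12.6%) is not. There is bias only if removal differs between arms and removed participants differ in pain. The change is worth making because it is cheap and closes the gap whatever the true rates are.

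**What to change.** In the protocol (Risk and Benefits, items 7 and 8):
- Delete non-compliance as a reason for leaving data collection.
- Separate stopping the study product, for any reason, from leaving the study.
- State that the 1- and 2-week assessments will be sought from every randomised participant who has not withdrawn consent.

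In the SAP:
- State that all randomised participants with a 2-week score are analysed in their assigned group regardless of compliance.
- Use the recorded nightly hours only for a supportive analysis.

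The cost is about three sentences and the effort of keeping visits for people who have stopped the product, over two weeks at most. Including non-compliers may slightly dilute the observed effect. Some scores will still be missing, so this does not replace a rule for missing data, which the SAP also lacks.

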1. * Describe the purpose, specific aims, or objectives and state the hypotheses to be tested:

The purpose of this study is to assess the efficacy of Theraworx foam in reduction of inflammation and pain as measured by subjective pain/disability scales, motion, and strength testing.

Specific Aim 1: To assess the efficacy of Theraworx foam in reduction of pain on subjective pain/disability scales for thumb CMC arthritis.

- Hypothesis 1a: Patients given the Theraworx foam and compression wrap will see significant improvements in reported Numeric Pain Rating Scale (NPRS) compared to patients who are given the placebo foam and compression wrap and Theraworx foam alone.
- Hypothesis 1b: Patients given the Theraworx foam and compression wrap will see significant improvements in score on the Disabilities of the Arm, Shoulder, and Hand (DASH) questionnaire compared to patients who are given the placebo foam and compression wrap and Theraworx foam alone.

Specific Aim 2: To assess the efficacy of Theraworx foam to improve function and patient reported outcomes for thumb CMC arthritis.

- Hypothesis 2a: Patients given the Theraworx foam and compression wrap will see significant improvements wrist range of motion compared to patients who are given the placebo foam and compression wrap and Theraworx foam alone.
- Hypothesis 2b: Patients given the Theraworx foam and compression wrap will see significant improvements in grip and pinch strength compared to patients who are given the placebo foam and compression wrap and Theraworx foam alone.

2. * Describe the relevant prior experience and gaps in current knowledge including preliminary data. Provide for the scientific or scholarly background for, rationale for, and significance of the research based on existing literature and how it will add to existing knowledge:

Recent research surrounding the structure and function of the outermost layers of

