Significance: If the Theraworx foam and/or Theraworx foam with compression wrap can be shown to reduce pain and allow for improved functional measures, the product can be proposed as an option for conservative treatment of thumb CMC OA and reduce the reliance on oral pain medications, steroid injections, and surgery.

Study Design

1. Total number of subjects to be enrolled at this site (enter -1 for chart reviews, banking, registries):

60

2. Describe and explain the study design:

After informed consent, subjects will be randomized to one of three groups:

1. Theraworx foam with compression wrap
2. Placebo foam with compression wrap
3. Theraworx foam alone

Baseline testing will include Numeric Pain Rating Scale (NPRS). The Disabilities of the Arm, Shoulder, and Hand (DASH) will be administered to the participant by the study coordinator. Static range of motion will be tested with a wrist goniometer measuring flexion, extension, ulnar deviation, and radial deviation with the participant's elbow supported on a hand table. Strength testing will be performed with a hand dynamometer and pinch meter. These questionnaires/tests will be performed at baseline, 1 week, and 2 week visits. They should take approximately 10 minutes to complete.

Subjects will be instructed to apply the foam every night (two pumps and rub into the base of the thumb). This will be demonstrated by the research coordinator (to be hired and added to this IRB application).

Participants will be asked to apply the foam nightly for a minimum of 6 and maximum 10 of hours and avoid use of lotions, topical creams, or topical NSAIDs during the study period. Subjects will be advised to avoid other oral prescription or OTC pain relief medications during the 2-week study period. A study data sheet will be given at this time for the participant to document nightly compliance hours, daily Tylenol use, and daily pain rating. This sheet will be collected at the 2 week visit. This portion of the research visit should take approximately 5 minutes but will allow for time for questions.

Randomization will occur via block randomization designed to randomize subjects into groups that result in equal sample sizes.

3. Describe the primary and secondary study endpoints:

All endpoints are primary:

1. Numeric Pain Rating Scale
2. Disabilities of the Arm, Shoulder, and Hand (DASH)
3. Pinch strength
4. Grip strength
5. Thumb range of motion

4. Provide a description of the following study timelines:

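### The SAP names one primary outcome (VAS pain at 2 weeks), the protocol calls five endpoints primary and measures pain by NPRS, and nothing says which governs or what counts as success

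*Combined protocol and SAP*

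**What the plan says.** **Statistical Analysis Plan.** "The Primary Outcome is VAS pain score at 2 weeks". It is to be analysed by ANOVA at 0.05. Secondary outcomes get the same test at the same level but are not listed.

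**Study Design, item 3.** "All endpoints are primary", followed by NPRS, DASH, pinch strength, grip strength and thumb range of motion. The list gives no time point and no success rule.

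**Pain instrument.** Hypothesis 1a, the baseline testing in Study Design item 2, the endpoint list, the power analysis and the Research Visits text all use the NPRS. The power analysis begins "The mean pain reported in subjects with CMC arthritis is 5 (out of 10) on the numeric pain rating scale". On timing, Research Activities item 1 says "These questionnaires/tests will be performed at the baseline, 1 week and 2 week visits". VAS occurs only in the SAP.

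**Motion.** Endpoint 5 is "Thumb range of motion". Hypothesis 2a predicts "significant improvements wrist range of motion", and the procedure reads "Static range of motion will be tested with a wrist goniometer measuring flexion, extension, ulnar deviation, and radial deviation".

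**The concern.** DASH, grip, pinch and motion cannot be both primary, as the protocol has them, and secondary, as the SAP implies. Once results are known, either section could be cited for what the trial set out to show. The SAP's primary outcome, read literally, also has no described source.

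The missing success rule matters on either reading of the five-endpoint list. If any one endpoint suffices, the false-positive rate exceeds the nominal 5%. If all five are needed, the joint power is below the power of any single endpoint. The trial was sized on pain alone.

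Separately, four wrist readings cannot support a conclusion about thumb motion, and nothing says how the four are to be combined.

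**Working it through.** **1. The plan's own sample size (Study Design, item 8).** Inputs: difference of 2 NPRS points, alpha 0.05, beta 0.2. No SD is given, so 16 per group cannot be derived from the stated inputs alone. With an assumed SD of 2 and a two-sided test:

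n = 2 × (1.960 + 0.842)² × (2/2)² = 15.7, so 16 per group.

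With 20% dropout, 16/0.8 = 20 per group and 3 × 20 = 60 in total, as planned. The calculation uses one endpoint, pain on the NPRS, at the full 0.05. It makes no allowance for five primaries.

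**2. If the SAP governs.** One primary outcome, one omnibus ANOVA at 0.05: 5% error.

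**3. If the list of five governs and any one endpoint suffices.** Each endpoint is tested at the SAP's 0.05.

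- Five independent tests: 1 − 0.95⁵ = 0.226. Upper bound: 5 × 0.05 = 0.25.
- Eight independent tests (NPRS, DASH, pinch, grip and four wrist directions tested separately): 1 − 0.95⁸ = 0.337. Upper bound: 8 × 0.05 = 0.40.

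The documents give no correlations between endpoints, so a range is assumed. Null trials with three arms of 16 were simulated, 60,000 per correlation, counting any ANOVA p < 0.05.

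**4. If all five must succeed.** Error stays at or below 5%. Assuming 80% power on each endpoint, joint power under independence is 0.8⁵ = 0.328. For correlated endpoints, one arm was shifted by 0.98 SD on every endpoint, which gives each ANOVA 80% power (60,000 trials per correlation).

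| Assumed pairwise correlation | Any of 5: false positive | Any of 8: false positive | All 5: joint power |
|---|---|---|---|
| 0 (formula) | 22.6% | 33.7% | 32.8% |
| 0.3 | 21.0% | 30.6% | 43.1% |
| 0.5 | 18.8% | 26.2% | 49.7% |
| 0.7 | 15.7% | 19.9% | 57.9% |

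Repeat simulations agreed to within about one percentage point.

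**5. Keeping five primaries with Bonferroni.** Alpha is 0.05/5 = 0.01. With the same assumed SD of 2, n = 2 × (2.576 + 0.842)² = 23.4, so 24 per group. With dropout, 24/0.8 = 30 per group, or 90 in total against 60 planned. Power at 16 per group would be about 60%. This takes the other four endpoints to have the same standardised effect as pain, which the documents do not state.

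**The case against.** The strongest reply is that the intent is clear enough. The SAP names pain, the sample size rests on pain, and VAS is probably loose wording for NPRS. On that reading the error on the primary omnibus test is 5%. This is the likely intent, but no text says so: nothing equates the two scales or ranks the two sections. Participants also keep a data sheet with a daily pain rating on an unnamed scale, collected at 2 weeks, so there is a second possible source for pain at that time.

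It is also fair that no document states an any-one or an all-five rule. The hypotheses are four separate statements, each with its own outcome. The 80% power per endpoint and the correlations are assumptions, and the eight-test case further supposes that each wrist direction is tested separately. The figures are therefore conditional illustrations and not the trial's actual error or power.

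On motion, the sponsor may have meant thumb motion and described the wrong measurement. That is possible, but Hypothesis 2a and both descriptions of the procedure refer to the wrist. Measuring the thumb would require a new procedure.

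Finally, Basic Information item 3 calls this a pilot, so strict control over secondary outcomes is partly a matter of choice. That supports an exploratory label. It does not excuse two conflicting definitions of primary, since the aims are framed as efficacy hypotheses.

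**Conclusion.** The concern holds and must be fixed. The current text contradicts itself on how many primary endpoints there are, names a pain scale that no described procedure uses, and labels as thumb motion something measured at the wrist.

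The size depends on the reading. It is 5% error if the SAP governs. If any of five endpoints suffices at 0.05, it is about 16% to 23% over assumed correlations from 0.7 down to 0, and never more than 25%. If all five are needed and each has 80% power, joint power is about 33% to 58% over correlations from 0 to 0.7. The contradiction itself rests on no assumption.

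**What to change.** 1. In both Study Design item 3 and the SAP, name one primary endpoint: NPRS pain at the 2-week visit. It is already collected and is the only endpoint the trial was sized on. Replace VAS with NPRS. Naming the visit assessment also rules out the daily data-sheet rating as the source.
2. List DASH, grip strength, pinch strength and range of motion by name as secondary. Either label them exploratory, which fits the pilot purpose, or control multiplicity. Holm is one option, with a first step of 0.05/4 = 0.0125 for four tests. In that case reduce the four wrist directions to one summary or count all of them in the family.
3. Rename endpoint 5 as wrist range of motion, to match Hypothesis 2a and the described measurement, and draw no conclusion on thumb motion.

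The cost is wording in two places, with no added subject, visit or procedure, and the planned 20 per group is unchanged. Four endpoints lose primary status and any claim about thumb motion is given up. This settles the endpoint only. A three-group omnibus ANOVA does not show which arm differs, so the comparison or comparisons that decide Hypothesis 1a must still be stated.
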